Dispense the next 12-week blister pack of teriflunomide or oral placebo

Timing and Sequence Considerations:

- Prior to infusion
 - Perform urine pregnancy test; *Must have confirmed negative prior to start of infusion*
 - All labs, and ADA, drawn prior to start of pre-treatment and infusion
 - PK
 - Physical examination, EDSS and clinical assessments pre-infusion

- MRI
 - 12 lead ECG
 - Vital signs
- During infusion
- Infusion log
- Post Infusion
- Additional PK 30 minutes +/- 15 minutes after end of infusion
 - 12 lead ECG

Visit:	Week 36 Day 252																								
Time Required:	Approximately 1 hour																								
Treatment:	 Teriflunomide (14 mg) or oral placebo until last day of Week 95																								
Tests:	 Urine Pregnancy Test; Must have confirmed negative result																								
Clinical Assessments:	 Adverse Event  Concomitant medications  Physical examination/vital signs  EDSS, MSFC and neurological examination																								
Labs: (see Laboratory Manual for full details, instructions, and shipping information)	 Hematologic profile; CBC/FBC with differential and platelet count  Serum chemistry panel; 
  
 Serum Chemistry	
   
 Albumin	Glucose	SGPT [ALT]	
 
 Alkaline phosphatase	LDH	Sodium	
 
 Bicarbonate	Magnesium	Total bilirubin	
 
 BUN	Phosphorus	Total Protein	
 
 Calcium	Potassium	Uric acid	
 
 Chloride	SGGT	Indirect/direct bilirubin	
 
 Creatinine	SGOT [AST]		
  
  Pancreatic Enzyme  Absolute B cell lymphocyte count and % B cell  Urinalysis	Serum Chemistry			Albumin	Glucose	SGPT [ALT]	Alkaline phosphatase	LDH	Sodium	Bicarbonate	Magnesium	Total bilirubin	BUN	Phosphorus	Total Protein	Calcium	Potassium	Uric acid	Chloride	SGGT	Indirect/direct bilirubin	Creatinine	SGOT [AST]	
Serum Chemistry																									
Albumin	Glucose	SGPT [ALT]																							
Alkaline phosphatase	LDH	Sodium																							
Bicarbonate	Magnesium	Total bilirubin																							
BUN	Phosphorus	Total Protein																							
Calcium	Potassium	Uric acid																							
Chloride	SGGT	Indirect/direct bilirubin																							
Creatinine	SGOT [AST]																								
Documents / Forms:	 eCRF documentation  Infusion Log  AE and SAE Reporting (If applicable)  Sample shipping  Teriflunomide or oral placebo dispensation  Subject diary review and teriflunomide/oral placebo accountability  Dispensing Subject Diary																								

Drug Preparation / Dispensation:

Dispense the next 12 week blister pack of teriflunomide or oral placebo

Visit: | **Week 48 Day 336**

Time Required: | Full day; *Approximately 3 – 5 hours plus time for MRI*

Treatment:

- Ublituximab 450 mg or placebo infusion in 250 mL volume; *1 hour infusion time*
 - Pre-medicate 30-60 minutes prior to each dose of ublituximab or IV placebo with an antihistamine (diphenhydramine 50 mg or equivalent), and corticosteroid (dexamethasone 10-20 mg or equivalent). Oral acetaminophen, 650 mg (or equivalent; only used for intervention) should be restricted to subject who experience fever or pyrexia after Week 1 dose, or as clinically warranted and additional medication (which needs to be documented) may be used at discretion of the physician if adverse reactions occur.
- Teriflunomide (14 mg) or oral placebo until last day of Week 95

Tests:

- 12 Lead ECG; *pre- and post-infusion*
- MRI; *See MRI Manual for full details and instructions (must be done before infusion)*
- Urine Pregnancy Test; *Must have confirmed negative result prior to start of infusion*

Clinical Assessments:

- Adverse Event
- Concomitant medications
- EDSS, MSFC, MSQOL54, SDMT, FIS and neurological examination
- Physical examination/vital signs

Labs:
(see Laboratory Manual for full details, instructions, and shipping information)

- Hematologic profile; *CBC/FBC with differential and platelet count*
- Serum chemistry panel;

Serum Chemistry

Albumin	Glucose	SGPT [ALT]
Alkaline phosphatase	LDH	Sodium
Bicarbonate	Magnesium	Total bilirubin
BUN	Phosphorus	Total Protein
Calcium	Potassium	Uric acid
Chloride	SGGT	Indirect/direct bilirubin
Creatinine	SGOT [AST]	

- Pancreatic Enzyme
- Absolute B cell lymphocyte count and % B cell
- Urinalysis
- Fibrinogen
- Quantitative Immunoglobulin; *Total Ig, IgG, IgM, IgA*
- Pharmacokinetics (for all subjects); *Prior to first infusion and at 30 minutes +/- 15 minutes after end of infusion on infusion day*
- Anti-Drug Antibodies; *Drawn prior to infusion*
- Teriflunomide Drug Concentration Test

**Documents /
Forms:**

- eCRF documentation
- Infusion Log
- AE and SAE Reporting (If applicable)
- Sample shipping
- Teriflunomide or oral placebo dispensation
- Subject diary review and teriflunomide/oral placebo accountability

- Dispensing Subject Diary

**Drug
Preparation /
Dispensation:**

For ublituximab or IV placebo (**See Pharmacy Manual**) 450 mg ublituximab diluted in 0.9% Normal Saline for total volume of 250 mg

Dispense the next 12-week blister pack of teriflunomide or oral placebo

**Timing and
Sequence
Considerations:**

Prior to infusion

- Perform urine pregnancy test; *Must have confirmed negative prior to start of infusion*
- All labs and ADA, drawn prior to start of pre-treatment and infusion
- PK
- Physical examination, EDSS and clinical assessments pre-infusion
- MRI
- 12 lead ECG
- Vital signs

During infusion

- Infusion log

Post Infusion

- Additional PK at 30 minutes +/- 15 minutes after end of infusion
- 12 lead ECG

Visit: | **Week 60 Day 420**

**Time
Required:** | Approximately 1 hour

Treatment: | Teriflunomide (14 mg) or oral placebo until last day of Week 95

Tests: | Urine Pregnancy Test; *Must have confirmed negative result*

**Clinical
Assessments:**

- Adverse Event
- Concomitant medications
- Physical examination/vital signs
- EDSS, MSFC and neurological examination

Labs:
(see
Laboratory

- Hematologic profile; *CBC/FBC with differential and platelet count*
- Serum chemistry panel;

Serum Chemistry

Manual for full details, instructions, and shipping information)	Albumin	Glucose	SGPT [ALT]
	Alkaline phosphatase	LDH	Sodium
	Bicarbonate	Magnesium	Total bilirubin
	BUN	Phosphorus	Total Protein
	Calcium	Potassium	Uric acid
	Chloride	SGGT	Indirect/direct bilirubin
	Creatinine	SGOT [AST]	

- Pancreatic Enzyme
- Absolute B cell lymphocyte count and % B cell
- Urinalysis

Documents / Forms:

- eCRF documentation
- Infusion Log
- AE and SAE Reporting (If applicable)
- Sample shipping
- Teriflunomide or oral placebo dispensation
- Subject diary review and teriflunomide/oral placebo accountability
- Dispensing Subject Diary

Drug Preparation / Dispensation:

Dispense the next 12-week blister pack of teriflunomide or oral placebo

Visit: | **Week 72 Day 504**

Time Required: | Full day; *Approximately 3 – 5 hours*

Treatment:

- Ublituximab 450 mg or placebo infusion in 250 mL volume; *1 hour infusion time*
 - Pre-medicate 30-60 minutes prior to each dose of ublituximab or IV placebo with an antihistamine (diphenhydramine 50 mg or equivalent), and corticosteroid (dexamethasone 10-20 mg or equivalent). Oral acetaminophen, 650 mg (or equivalent; only used for intervention) should be restricted to subject who experience fever or pyrexia after Week 1 dose, or as clinically warranted and additional medication (which needs to be documented) may be used at discretion of the physician if adverse reactions occur.
- Teriflunomide (14 mg) or oral placebo until last day of Week 95

Tests:

- 12 Lead ECG; *pre- and post-infusion*
- Urine Pregnancy Test; *Must have confirmed negative result prior to start of infusion*

Clinical Assessments:

- Adverse Event
- Concomitant medications
- EDSS, MSFC and neurological examination
- Physical examination/vital signs

Labs:

- Hematologic profile; *CBC/FBC with differential and platelet count*
- Serum chemistry panel;

(see Laboratory Manual for full details, instructions, and shipping information)

Serum Chemistry		
Albumin	Glucose	SGPT [ALT]
Alkaline phosphatase	LDH	Sodium
Bicarbonate	Magnesium	Total bilirubin
BUN	Phosphorus	Total Protein
Calcium	Potassium	Uric acid
Chloride	SGGT	Indirect/direct bilirubin
Creatinine	SGOT [AST]	

- Pancreatic Enzyme
- Absolute B cell lymphocyte count and % B cell
- Urinalysis
- Fibrinogen
- Quantitative Immunoglobulin; *Total Ig, IgG, IgM, IgA*
- Pharmacokinetics (for all subjects); *Prior to first infusion and at 30 minutes +/- 15 minutes after end of infusion*
- Anti-Drug Antibodies; *Drawn prior to infusion*

Documents / Forms:

- eCRF documentation
- Infusion Log
- AE and SAE Reporting (If applicable)
- Sample shipping
- Teriflunomide or oral placebo dispensation
- Subject diary review and teriflunomide/oral placebo accountability
- Dispensing Subject Diary

Drug Preparation / Dispensation:

For ublituximab or IV placebo (**See Pharmacy Manual**) 450 mg ublituximab diluted in 0.9% Normal Saline for total volume of 250 mg
 Dispense the next 12-week blister pack of teriflunomide or oral placebo

Timing and Sequence Considerations:

- Prior to infusion
- Perform urine pregnancy test; *Must have confirmed negative prior to start of infusion*
 - All labs and ADA, drawn prior to start of pre-treatment and infusion
 - PK
 - Physical examination, EDSS and clinical assessments pre-infusion
 - 12 lead ECG
 - Vital signs
- During infusion
- Infusion log
- Post Infusion
- Additional PK at 30 minutes +/- 15 minutes after end of infusion
 - 12 lead ECG

Visit: | Week 84 Day 588

Time Required:	Approximately 1 hour																								
Treatment:	 Teriflunomide (14 mg) or oral placebo until last day of Week 95																								
Tests:	 Urine Pregnancy Test; Must have confirmed negative result																								
Clinical Assessments:	 Adverse Event  Concomitant medications  Physical examination/vital signs  EDSS, MSFC and neurological examination																								
Labs: (see Laboratory Manual for full details, instructions, and shipping information)	 Hematologic profile; CBC/FBC with differential and platelet count  Serum chemistry panel; 
  
 Serum Chemistry	
   
 Albumin	Glucose	SGPT [ALT]	
 
 Alkaline phosphatase	LDH	Sodium	
 
 Bicarbonate	Magnesium	Total bilirubin	
 
 BUN	Phosphorus	Total Protein	
 
 Calcium	Potassium	Uric acid	
 
 Chloride	SGGT	Indirect/direct bilirubin	
 
 Creatinine	SGOT [AST]		
  
  Pancreatic Enzyme  Absolute B cell lymphocyte count and % B cell  Urinalysis	Serum Chemistry			Albumin	Glucose	SGPT [ALT]	Alkaline phosphatase	LDH	Sodium	Bicarbonate	Magnesium	Total bilirubin	BUN	Phosphorus	Total Protein	Calcium	Potassium	Uric acid	Chloride	SGGT	Indirect/direct bilirubin	Creatinine	SGOT [AST]	
Serum Chemistry																									
Albumin	Glucose	SGPT [ALT]																							
Alkaline phosphatase	LDH	Sodium																							
Bicarbonate	Magnesium	Total bilirubin																							
BUN	Phosphorus	Total Protein																							
Calcium	Potassium	Uric acid																							
Chloride	SGGT	Indirect/direct bilirubin																							
Creatinine	SGOT [AST]																								
Documents / Forms:	 eCRF documentation  Infusion Log  AE and SAE Reporting (If applicable)  Sample shipping  Teriflunomide or oral placebo dispensation  Subject diary review and teriflunomide/oral placebo accountability  Dispensing Subject Diary																								
Drug Preparation / Dispensation:	Dispense the next 12-week blister pack of teriflunomide or oral placebo																								
Visit:	Week 96 Day 672																								
Time Required:	Full day; Approximately 3 – 5 hours plus time for MRI																								
Treatment:	None																								
Tests:	 MRI; See MRI Manual for full details and instructions																								

Urine Pregnancy Test; *Must have confirmed negative result*

Clinical Assessments:

- Adverse Event
- Concomitant medications
- EDSS, MSFC, MSQOL54, SDMT, FIS and neurological examination
- Physical examination/vital signs

Labs:
(see Laboratory Manual for full details, instructions, and shipping information)

- Hematologic profile; *CBC/FBC with differential and platelet count*
- Serum Chemistry Panel;

Serum Chemistry

Albumin	Glucose	SGPT [ALT]
Alkaline phosphatase	LDH	Sodium
Bicarbonate	Magnesium	Total bilirubin
BUN	Phosphorus	Total Protein
Calcium	Potassium	Uric acid
Chloride	SGGT	Indirect/direct bilirubin
Creatinine	SGOT [AST]	

- Pancreatic Enzyme
- Absolute B cell lymphocyte count and % B cell
- Urinalysis
- Quantitative Immunoglobulin; *Total Ig, IgG, IgM, IgA*
- Pharmacokinetics (for all subjects); *Prior to first infusion and at 30 minutes +/- 15 minutes after end of infusion*
- Anti-Drug Antibodies; *Drawn prior to infusion*
- Teriflunomide Drug Concentration Test

Documents / Forms:

- eCRF documentation
- Infusion Log
- AE and SAE Reporting (If applicable)
- Sample shipping
- Teriflunomide or oral placebo accountability

Visit: **Week 100 Day 700**

Time Required: Approximately 1 hour

Treatment: Initiate the teriflunomide rapid elimination process (11 days) via activated charcoal or cholestyramine

Tests: Urine Pregnancy Test

Clinical Assessments:

- Adverse Event
- Concomitant medications
- Physical examination/vital signs

Labs:
(see
Laboratory
Manual for full
details,
instructions,
and shipping
information)

- Hematologic profile; *CBC/FBC with differential and platelet count*
- Serum chemistry panel;

Serum Chemistry

Albumin	Glucose	SGPT [ALT]
Alkaline phosphatase	LDH	Sodium
Bicarbonate	Magnesium	Total bilirubin
BUN	Phosphorus	Total Protein
Calcium	Potassium	Uric acid
Chloride	SGGT	Indirect/direct bilirubin
Creatinine	SGOT [AST]	

- Pancreatic Enzyme
- Absolute B cell lymphocyte count and % B cell
- Urinalysis

**Documents /
Forms:**

- eCRF documentation
- AE and SAE Reporting (If applicable)
- Sample shipping
- Dispensing Subject Diary for elimination drug accountability

Visit: | **Week 104 Day 728**

**Time
Required:** | Approximately 1 hour

Treatment: | None

Tests: | Urine pregnancy test; *must be negative*

**Clinical
Assessments:**

- Adverse Event
- Concomitant medications
- Physical examination/vital signs

Labs:
(see
Laboratory
Manual for full
details,
instructions,
and shipping
information)

- Hematologic profile; *CBC/FBC with differential and platelet count*
- Serum chemistry panel;

Serum Chemistry

Albumin	Glucose	SGPT [ALT]
Alkaline phosphatase	LDH	Sodium
Bicarbonate	Magnesium	Total bilirubin
BUN	Phosphorus	Total Protein
Calcium	Potassium	Uric acid
Chloride	SGGT	Indirect/direct bilirubin
Creatinine	SGOT [AST]	

- Pancreatic Enzyme
- Absolute B cell lymphocyte count and % B cell
- Urinalysis

Documents / Forms: eCRF documentation
 AE and SAE Reporting (If applicable)
 Sample shipping
 Acknowledgement of completion of teriflunomide elimination program

Drug Preparation / Dispensation: None

Visit: **Week 108 Day 756**

Time Required: Approximately < 1 hour; *this will be done over the phone*

Treatment: None

Tests: Urine Pregnancy Test

Clinical Assessments: Adverse Event
 Concomitant medications

Labs: None
(see Laboratory Manual for full details, instructions, and shipping information)

Documents / Forms: eCRF documentation; *completed by staff at study site*
 AE and SAE Reporting (If applicable)
 Study staff to remind all subjects of the importance of using contraception throughout the study

Drug Preparation / Dispensation: None

Visit: **Week 112 Day 784**

Time Required: Approximately < 1 hour; *this will be done over the phone*

Treatment:	None
Tests:	 Urine Pregnancy Test
Clinical Assessments:	 Adverse Event  Concomitant medications
Labs: (see Laboratory Manual for full details, instructions, and shipping information)	None
Documents / Forms:	 eCRF documentation; completed by staff at study site  AE and SAE Reporting (If applicable)  Study staff to remind all subjects of the importance of using contraception throughout the study
Drug Preparation / Dispensation:	None
Visit:	Week 116 Day 812
Time Required:	Approximately < 1 hour
Treatment:	None
Tests:	 Urine Pregnancy Test
Clinical Assessments:	 Adverse Event  Concomitant medications  Physical examination/vital signs
Labs: (see Laboratory Manual for full details, instructions, and shipping information)	 Teriflunomide Drug Concentration Test. Prior to discharge from the study, all subjects will be counseled by the treating team to have their teriflunomide plasma concentration re-measured prior to attempting to become pregnant or trying to impregnate a female partner.

Documents / Forms: eCRF documentation
 AE and SAE Reporting (If applicable)

Drug Preparation / Dispensation: None

Visit: **Unscheduled Relapse Visit**

Time Required: Full day; *Approximately 3 - 5 hours*

Treatment: None

Tests: Serum Pregnancy Test; *must be negative results*

Clinical Assessments: Adverse Event
 Concomitant medications
 EDSS Assessment
 Physical examination/vital signs

Hematologic profile; *CBC/FBC with differential and platelet count*
 Serum chemistry panel;

Labs:
(see Laboratory Manual for full details, instructions, and shipping information)

Serum Chemistry		
Albumin	Glucose	SGPT [ALT]
Alkaline phosphatase	LDH	Sodium
Bicarbonate	Magnesium	Total bilirubin
BUN	Phosphorus	Total Protein
Calcium	Potassium	Uric acid
Chloride	SGGT	Indirect/direct bilirubin
Creatinine	SGOT [AST]	

Pancreatic Enzyme
 Absolute B cell lymphocyte count and % B cell
 Urinalysis
 Fibrinogen
 Quantitative Immunoglobulin; *Total Ig, IgG, IgM, IgA*

Documents / Forms: Informed Consent Form
 eCRF documentation
 AE and SAE Reporting (If applicable)
 Sample shipping
 Teriflunomide or oral placebo accountability

Drug Preparation / Dispensation: None

Timing and Sequence Considerations: | Once signed consent is obtained, procedures can be scheduled for the day at Investigator and subject convenience.

Visit: | **Early Withdrawal from Treatment**

Time Required: | Full day; *Approximately 3 – 5 hours plus time for MRI*

Treatment: | Initiate the teriflunomide rapid elimination process (11 days) via activated charcoal or cholestyramine

Tests: | Serum Pregnancy Test; *must be negative results*
 MRI
 12 lead ECG

Clinical Assessments: | Adverse Event
 Concomitant medications
 EDSS, MSFC, MSQOL54, SDMT, FIS and neurological examination
 Physical examination/vital signs

Labs: | Hematologic profile; *CBC/FBC with differential and platelet count*
 Serum chemistry panel;

Labs:
 (see Laboratory Manual for full details, instructions, and shipping information)

Serum Chemistry		
Albumin	Glucose	SGPT [ALT]
Alkaline phosphatase	LDH	Sodium
Bicarbonate	Magnesium	Total bilirubin
BUN	Phosphorus	Total Protein
Calcium	Potassium	Uric acid
Chloride	SGGT	Indirect/direct bilirubin
Creatinine	SGOT [AST]	

Pancreatic Enzyme
 Absolute B cell lymphocyte count and % B cell
 Urinalysis
 Fibrinogen
 Teriflunomide Drug Concentration Test
 Quantitative Immunoglobulin

Documents / Forms: | Informed Consent Form
 eCRF documentation
 AE and SAE Reporting (If applicable)
 Sample shipping
 Subject diary review and teriflunomide or oral placebo accountability

Drug Preparation / Dispensation: | None

**Timing and
Sequence
Considerations:**

Once signed consent is obtained, procedures can be scheduled for the day at Investigator and subject convenience.

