4.4 GENERAL CONCOMITANT MEDICATION AND SUPPORTIVE CARE GUIDELINES

The following treatments are prohibited while on clinical trial: other investigational drug treatments or interventional study participation, other DMTs used to treat MS, radiation therapy, hormonal therapy for cancer, cancer immunotherapy or other biologic therapy excluding study medication. The exceptions to this are:

- No glucocorticoids may be administered outside of protocol requirements for pre-medication or AE management, except low doses of steroids stabilized at ≤ 10 mg per day of prednisone or equivalent, and started at least 7 days prior to study entry (Screening).

Antiemetic for Ublituximab or IV placebo: Ublituximab or IV placebo is considered to be of low emetogenic potential that may be adequately prevented with prochlorperazine. Other antiemetic may be used at the discretion of the Treating Neurologist/PI if nausea and/or vomiting is not adequately controlled/prevented.

Pre-medication prior to infusion with ublituximab or IV placebo: Infusion Related Reactions have been reported with ublituximab or IV placebo with more profound reactions in subjects with hematologic malignancies. All subjects treated with ublituximab or IV placebo require pre-medication 30–60 minutes prior to each dose of ublituximab or IV placebo with an antihistamine (diphenhydramine 50 mg or equivalent; administered orally), and a corticosteroid (dexamethasone 10-20 mg or equivalent; administered orally).

Treatment of IRR: Symptomatic infusion reactions despite pre-medication, may be treated at the discretion of the treating physician, including but not limited to: oral acetaminophen 650 mg (only used for intervention), corticosteroids, antihistamines, oxygen and bronchodilators.

Note: In case the above referenced medications are not available, equivalents can be used at the investigator's discretion. If medications are given intravenously, the IV line used for ublituximab/IV placebo should not be used. If needed, please consult the Medical Monitor.

Antihypertensive Medications: Since infusion related hypotension may occur, the investigator should carefully consider withholding anti-hypertensive medication during the 24 hours prior to, and throughout the IV infusion of ublituximab or placebo.

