⁴ Weeks 8 and beyond, collections/assessments may occur ± 5 days from specified time points, except for MRI scans, which can occur ± 7 days on Weeks 12 and 96 and must be performed pre-infusion on infusion days (- 7 days) on Weeks 24 and 48. MRI scan at Early Withdrawal from Treatment Visit should be performed within 4 weeks after withdrawing from the study.

⁵ Prior to each infusion except PT/INR which is completed at baseline. Urine Pregnancy Test on non-infusion days subjects will test upon arrival at the site

⁶ Prior to infusion and 30 minutes +/- 15 minutes post-infusion on infusion days. For non-infusion days, one PK sample should be obtained

⁷ Anti-Drug Antibodies are antibodies developed against ublituximab

⁸ Physical examination will occur on all visits except Week 1 Day 2 and Week 2 Day 8

⁹ Within 2 hours pre-infusion and 60 minutes +/- 15 minutes post-infusion on any infusion day

¹⁰ Re-consent following a suspected relapse is required if the relapse is confirmed by IRAP or by the Treating Neurologist (Treating Neurologist medically confirmed relapse), whichever comes first. Re-consent must occur within 6 weeks after first reporting of relapse. Re-consent may occur at the next schedule office visit but may require an unscheduled visit if the relapse occurs between Weeks 24 and 96 (where the frequency of scheduled visits is every 12 weeks).

¹¹ Serum pregnancy test must be completed within 5 days prior to Week 1 Day 1

¹² Obtain blood sample for teriflunomide drug concentration test prior to first dose of accelerated teriflunomide elimination procedure

¹³ Prior to each infusion

¹⁴ The Unscheduled Relapse Visit will be conducted if a possible relapse is reported by the subject. The visit is to be planned as soon as possible, within 7 days from subject notification of the relapse to the site. Infusion visit is delayed until relapse is back to baseline, or Treating Neurologist/PI does not expect any improvements.

¹⁶ Teriflunomide/oral placebo administration shall be taken in the morning until the last day of Week 95. Alternative dosing times are allowed if necessary.

¹⁷ Sample for teriflunomide concentration to be collected before the first oral dose of teriflunomide/oral placebo

¹⁸ For Unscheduled Relapse Visit, EDSS assessment (by Examining Neurologist) and neurological examination (by Treating Neurologist) will be performed independently

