¹⁹ Acknowledge completion of 11-day accelerated teriflunomide elimination procedure started at week 100

²⁰ If the subject experiences neutropenia, thrombocytopenia, anemia, or elevated liver enzymes, follow guidelines and procedures on laboratory retests and study treatment per Section 5.2.

²¹ Post Week 24 (including during the Follow-Up Period), urine pregnancy test will be administered every 4 weeks (+/- 5 days). On days when there is not a study visit, the subject will need to perform the test at home and contact the study site to provide the outcome

²² Week 1/Day 1 EDSS must be assessed within 1 day prior to randomization (i.e., on the day before randomization or on the day of randomization but before randomization occurs)

²³ Start 11-day accelerated teriflunomide elimination procedure the day after the early withdraw from treatment visit is completed

²⁴ Pre-medicate 30-60 minutes prior to each infusion of ublituximab/IV placebo with an anti-histamine (diphenhydramine 50 mg or equivalent) and corticosteroid (dexamethasone 10-20 mg or equivalent)

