Visit:	Week 24 Day 168																								
Time Required:	Full day; Approximately 3 - 5 hours plus time for MRI																								
Treatment:	 Ublituximab 450 mg or IV placebo infusion in 250 mL volume; 1 hour infusion time 
 Pre-medicate 30-60 minutes prior to each dose of ublituximab or IV placebo with an antihistamine (diphenhydramine 50 mg or equivalent), and corticosteroid (dexamethasone 10-20 mg or equivalent). Oral acetaminophen, 650 mg (or equivalent; only used for intervention) should be restricted to subject who experience fever or pyrexia after Week 1 dose, or as clinically warranted and additional medication (which needs to be documented) may be used at discretion of the physician if adverse reactions occur. 																								

Teriflunomide (14 mg) or oral placebo until last day of Week 95

Tests:

- 12 Lead ECG; *pre- and post-infusion*
- MRI; *See MRI Manual for full details and instructions (must be done before infusion)*
- Urine Pregnancy Test; *Must have confirmed negative result prior to start of infusion*

Clinical Assessments:

- Adverse Event
- Concomitant medications
- EDSS, MSFC, MSQOL54, SDMT, FIS and neurological examination
- Physical examination/vital signs

Labs:
(see Laboratory Manual for full details, instructions, and shipping information)

- Hematologic profile; *CBC/FBC with differential and platelet count*
- Serum chemistry panel;

Serum Chemistry

Albumin	Glucose	SGPT [ALT]
Alkaline phosphatase	LDH	Sodium
Bicarbonate	Magnesium	Total bilirubin
BUN	Phosphorus	Total Protein
Calcium	Potassium	Uric acid
Chloride	SGGT	Indirect/direct bilirubin
Creatinine	SGOT [AST]	

- Pancreatic Enzyme
- Absolute B cell lymphocyte count and % B cell
- Urinalysis
- Fibrinogen
- Quantitative Immunoglobulin; *Total Ig, IgG, IgM, IgA*
- Pharmacokinetics (for all subjects); *Prior to first infusion and at 30 minutes +/- 15 minutes after end of infusion on infusion days*
- Anti-Drug Antibodies; *Drawn prior to infusion*

Documents / Forms:

- eCRF documentation
- Infusion Log
- AE and SAE Reporting (If applicable)
- Sample shipping
- Teriflunomide or oral placebo dispensation
- Subject diary review and teriflunomide/oral placebo accountability
- Dispensing Subject Diary

Drug Preparation / Dispensation:

For ublituximab or IV placebo (**See Pharmacy Manual**) 450 mg ublituximab diluted in 0.9% Normal Saline for total volume of 250 mg

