#### 2.4.3.4 SDMT

The total score at one visit is defined as the total number of correct answers reported in the CRF. Impaired SDMT is defined as a decrease from baseline of at least four points at any post-baseline SDMT assessment up to the Week 96 visit. The proportion of impaired SDMT will be analyzed in all subjects within the modified intention to treat (mITT) population.

SDMT rates will be compared using logistic regression [REDACTED] with baseline adjustments the same as used in the primary endpoint analysis, without treatment duration offset, but including log-transformed baseline MRI counts (T1 unenhancing, T2, Gad enhancing). To avoid zero values for the log transformation of MRI counts, 1 will be added to each observation before transforming

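### On infusion days SDMT and the other clinical tests need only precede the infusion, not the premedication, which may add noise to SDMT impairment (key secondary endpoint 5)

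*Protocol*

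**What the plan says.** Protocol Appendix F gives a sequence list for each infusion visit. At Week 1 Day 1 and Week 24 the laboratory line reads "All labs, and ADA, drawn prior to start of pre-treatment and infusion"; at Weeks 48 and 72 it reads "All labs and ADA, drawn prior to start of pre-treatment and infusion". The line for clinical testing in the same lists is "Physical examination, EDSS and clinical assessments pre-infusion". The infusion is named separately in the laboratory line, so pre-treatment there can only sensibly mean premedication.

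Footnote 13 to the schedule in Section 6, attached to the EDSS/MSFC row and to the MSQoL-54/SDMT/FIS row in Tables 5 and 6, says only "Prior to each infusion". Footnote 5, also attached to the SDMT row in Table 6, sets the same limit.

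On premedication, Section 4.4 states "All subjects treated with ublituximab or IV placebo require pre-medication", given orally 30 to 60 minutes before each dose. It consists of an antihistamine (diphenhydramine 50 mg or equivalent) and a corticosteroid (dexamethasone 10-20 mg or equivalent).

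SAP Section 2.4.3.4 defines impaired SDMT as "a decrease from baseline of at least four points at any post-baseline SDMT assessment" up to Week 96. Protocol Section 8.9.2 agrees.

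**The concern.** The lists use two different limits, and the looser one applies to the efficacy tests. A site that uses the wait between premedication and infusion for SDMT or MSFC complies fully with the protocol. Neither document asks for the order to be recorded or allowed for in the analysis.

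SDMT is a 90-second speed test (protocol Section 6.3.5). If premedication lowers the score for a short time, a test affected at follow-up can count a subject as impaired, and a test affected at baseline can hide a real decline. The definition needs no confirmation, so nothing later corrects either error.

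SDMT impairment is fifth in a fixed testing sequence (SAP Section 2.4.3.1). Power lost there also puts at risk the confirmatory test of brain volume, which comes sixth.

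**Working it through.** The plan states no figure on this point, so there is none to reproduce. The check compares visits with infusion days, then illustrates the possible size.

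**Which tests are exposed**

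Infusion days are Week 1 Day 1, Week 3 Day 15, and Weeks 24, 48 and 72 (protocol Section 7.5.3). A test done in the gap falls between 0 and 60 minutes after premedication.

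- SDMT is scheduled at Week 1 Day 1 and Weeks 24, 48 and 96 (Tables 5 to 7). Three of the four are infusion days. SDMT is not done at Week 72. Baseline SDMT is not required to precede randomization, and the SAP's baseline rule (Section 2.1.3) works by date.
- EDSS after baseline is scheduled at Weeks 12, 24, 36, 48, 60, 72, 84 and 96. Three of the eight are infusion days. Baseline EDSS must be done before randomization (Sections 6.1 and 6.3.2), so the gap does not reach it.
- For 12-week CDP the onset and confirmation pairs are 12-24, 24-36, 36-48, 48-60, 60-72, 72-84 and 84-96. None has both visits on infusion days. Under SAP Section 2.4.3.5 (confirmation 12 weeks later) a transient effect cannot produce an event alone; it can alter only one reading of a pair.
- For 24-week CDP (tertiary), the pairs 24-48 and 48-72 both fall wholly on infusion days.
- MSFC (tertiary) is done at Week 1 Day 1 and Weeks 24, 48 and 72, among other visits.

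**Illustration for SDMT (every SDMT input is assumed)**

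Score = 50 + true change + normal error with within-subject SD s, minus a shift d on infusion days with probability 0.5, rounded. Impaired = baseline minus follow-up of at least 4 at Week 24, 48 or 96. Teriflunomide has no true change; ublituximab gains 1 point at each follow-up. Power is for two unadjusted proportions, 220 per arm, two-sided 0.05. Values for d = 1 / 2 / 3 points:

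| s | Quantity | No shift | Follow-up only affected | Baseline and follow-up affected |
|---|---|---|---|---|
| 2 | Impaired, no true change | 23.5% | 28.5 / 35.8 / 44.6% | 22.9 / 24.5 / 27.9% |
| 2 | Power | 0.79-0.80 | 0.82 / 0.84 / 0.85 | 0.77 / 0.73 / 0.66 |
| 3 | Impaired, no true change | 39.7% | 43.5 / 47.9 / 53.4% | 38.5 / 38.3 / 39.0% |
| 3 | Power | 0.57-0.59 | 0.59 / 0.59 / 0.58 | 0.55 / 0.55 / 0.48 |
| 4 | Impaired, no true change | 48.8% | 51.8 / 55.0 / 58.6% | 47.7 / 47.0 / 46.9% |
| 4 | Power | 0.39-0.40 | 0.37 / 0.39 / 0.37 | 0.39 / 0.37 / 0.33 |

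Simulation error in power is about 0.02. When only follow-up is affected, the impairment rate rises and power hardly moves. When baseline is affected too, the rate moves less and power falls.

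A second set assumes a larger effect: a linear course to -1.5 v +1.5 points at Week 96, with half of infusion-day tests, baseline included, after premedication. For d = 0 / 2 / 4, power is 97 / 90 / 71% (s = 3), 84 / 75 / 62% (s = 4) and 64 / 59 / 48% (s = 5).

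Both sets draw the order afresh at each visit. At s = 4, over four assumed trajectories, keeping the order fixed within a subject cuts the loss from a 4-point shift to about 3-10 percentage points of power, against 11-24 with independent draws. If only 10% of tests are exposed, a 2-point shift costs about 1-4 points.

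**The case against.** The strongest reply is that the harm is not shown. Neither document gives an effect of premedication on SDMT, MSFC or EDSS, an equivalent antihistamine may be used, and nothing shows that sites test in the gap. Clinical review before premedication is also the natural order: dosing depends on an acceptable clinical assessment (Section 5), relapse is assessed at every scheduled visit (Section 6.8), and a suspected relapse postpones the infusion visit (Section 5.2). Footnote 4 allows a window of 5 days either way from Week 8, so testing need not always fall on the infusion day.

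Most of this stands, and it limits the weight of the point. It does not close the gap for SDMT, which may be delegated to another team member (Section 6.3.5) and is not needed to decide on dosing.

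A reader might infer four stronger things that the documents do not support:

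- **That 12-week CDP is exposed as SDMT is.** Baseline EDSS is anchored before randomization, and each 12-week pair includes a non-infusion visit. Exposure would grow only if the protocol's wording (at least 12 weeks) were read to let a later visit confirm. The exclusion of rises due to concomitant medication adds little protection, since the EDSS rater is blinded to medication (Section 4.1.4) and the SAP's 12-week definition omits it.
- **That tests are run 30 to 60 minutes after premedication.** That interval separates premedication from infusion; a test in the gap may come at any point from 0 to 60 minutes.
- **That a loss of power is established.** It rests wholly on assumed inputs and nearly vanishes in some scenarios.
- **That the comparison is biased.** Both arms are premedicated under the same double-dummy schedule.

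**Conclusion.** The point holds as a minor gap with a cheap remedy. The protocol protects laboratory samples from premedication and leaves the clinical tests on the same pages unprotected; no other section closes the gap for SDMT, MSFC or post-baseline EDSS.

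SDMT impairment is the endpoint that matters here. Twelve-week CDP is marginally affected, and NEDA only through its CDP component. Twenty-four-week CDP and MSFC are also touched, but both are tertiary.

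The effect may be noise or dilution of unknown size. It depends on how often sites test after premedication, whether the order is consistent within a subject, whether baseline is affected, and how far premedication shifts the score. None of these is in the documents, so the power figures show a range of possibilities and are not estimates for this trial.

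**What to change.** On the Appendix F infusion-visit pages, require the tests below to be completed before pre-treatment starts, in the words already used for samples ("All labs and ADA, drawn prior to start of pre-treatment and infusion"):

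- SDMT, FIS and MSQoL-54: Week 1 Day 1, Weeks 24 and 48.
- MSFC and neurological examination: Week 1 Day 1, Weeks 24, 48 and 72.
- EDSS: Weeks 24, 48 and 72. The Week 1 EDSS keeps its existing anchor before randomization.

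Make the same change to footnotes 5 and 13 where they apply to these tests. Both also govern other rows, so a separate footnote for the clinical tests would be cleaner.

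This alters only the order of assessments; premedication and dosing stay as they are. The cost is one phrase per page and footnote, plus minor scheduling effort on infusion days. No procedure or staff are added.
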